**CONFIDENTIAL**

201334 [DTPA (BOOSTRIX)-049 BST: 048]

Protocol Amendment 1 Final

System	Component	Method	Kit / Manufacturer	Unit	Cut-off**	Laboratory †
						Biologicals*
SER	Haemophilus influenzae type b.Polyribosyl Ribitol Phosphate Ab	ELI	NA	µg/ml	0.15	GSK Biologicals*
SER	Streptococcus pneumoniae.Polysaccharide 01 Ab.IgG Streptococcus pneumoniae.Polysaccharide 03 Ab.IgG Streptococcus pneumoniae.Polysaccharide 05 Ab.IgG Streptococcus pneumoniae.Polysaccharide 06A Ab.IgG Streptococcus pneumoniae.Polysaccharide 06B Ab.IgG Streptococcus pneumoniae.Polysaccharide 07F Ab.IgG Streptococcus pneumoniae.Polysaccharide 09V Ab.IgG Streptococcus pneumoniae.Polysaccharide 14 Ab.IgG Streptococcus pneumoniae.Polysaccharide 18C Ab.IgG Streptococcus pneumoniae.Polysaccharide 19A Ab.IgG Streptococcus pneumoniae.Polysaccharide 19F Ab.IgG Streptococcus pneumoniae.Polysaccharide 23F Ab.IgG	ELIF or multiplex	NA	µg/ml	0.05 or equivalent cut-off for the multiplex	GSK Biologicals*

**CONFIDENTIAL**

201334 [DTPA (BOOSTRIX)-049 BST: 048]

Protocol Amendment 1 Final

System	Component	Method	Kit / Manufacturer	Unit	Cut-off**	Laboratory †
SER	Streptococcus pneumoniae.Polysaccharide 01 Ab.IgG	ELI	NA	µg/ml	0.15	WHO reference laboratory**
	Streptococcus pneumoniae.Polysaccharide 03 Ab.IgG					
	Streptococcus pneumoniae.Polysaccharide 04 Ab.IgG					
	Streptococcus pneumoniae.Polysaccharide 05 Ab.IgG					
	Streptococcus pneumoniae.Polysaccharide 06A Ab.IgG					
	Streptococcus pneumoniae.Polysaccharide 06B Ab.IgG					
	Streptococcus pneumoniae.Polysaccharide 07F Ab.IgG					
	Streptococcus pneumoniae.Polysaccharide 09V Ab.IgG					
	Streptococcus pneumoniae.Polysaccharide 14 Ab.IgG					
	Streptococcus pneumoniae.Polysaccharide 18C Ab.IgG					
	Streptococcus pneumoniae.Polysaccharide 19A Ab.IgG					
	Streptococcus pneumoniae.Polysaccharide 19F Ab.IgG					
	Streptococcus pneumoniae.Polysaccharide 23F Ab.IgG					

\*GSK Biologicals laboratory refers to the Clinical Laboratory Sciences (CLS) in Rixensart, Belgium; Wavre, Belgium; Neomed Lab Inc, Canada.

\*\* At the discretion of GSK Biologicals, pneumococcal testing may be done at a GSK Biologicals laboratory or the WHO reference laboratory

\*\*\* **Assay cut-off and unit might be subject to change during the course of the study (e.g. in case of requalification, revalidation or standardization). In this case, this will be documented in the clinical report.**

† Refer to the [APPENDIX A](#) for the laboratory addresses.

SER = Serum

ELI = Enzyme-linked immunosorbent assay (ELISA)

ELIF = 22F Inhibition ELISA

NEU = Neutralisation assay

CLIA = ChemiLuminescence ImmunoAssay

IU/mL = International Units/millilitre

mIU/mL = milliInternational Units/millilitre

EL.U/mL = ELISA Units/millilitre

µg/ml = Micrograms/millilitre

The GSK Biologicals’ clinical laboratories have established a Quality System supported by procedures. The activities of GSK Biologicals’ clinical laboratories are audited regularly for quality assessment by an internal (sponsor-dependent) but laboratory-independent Quality Department.

**5.7.4. Biological samples evaluation**

**5.7.4.1. Immunological read-outs**

The immunological read-outs are presented in [Table 8](#).

**Table 8 Immunological read-outs**

**(Amended 12 December 2016)**

Blood sampling time point		No. subjects	Component	Components priority rank
Type of contact and time point	Sampling time point			
Visit 2 ( Day 0 )	Pre-Bst	All	PT, FHA, PRN	1
			D, T	2
			HBs, PRP	3
			Poliovirus types 1, 2, 3	4
			13 pneumococcal serotypes	5
Visit 3 ( Day 30 )	Post-Bst	All	PT, FHA, PRN	1
			HBs, PRP	2
			D, T	3
			Poliovirus types 1, 2, 3	4
			13 pneumococcal serotypes	5

Pre-Bst: Blood sample to be collected before the booster dose.

Post-Bst: Blood sample to be collected one month after the booster dose

In case of insufficient blood sample volume to perform assays for all antibodies, the samples will be analysed according to priority ranking provided in [Table 8](#).

**5.7.5. Immunological correlates of protection**

The following cut-offs are accepted as immunological correlates of protection:

- Specific antibodies against diphtheria toxoid (anti-diphtheria) and tetanus toxoid (anti-tetanus) will be measured by Enzyme-linked immunosorbent assay (ELISA), for which the threshold of 0.1 International Units per ml (IU/ml) provides a conservative estimate of the percentage of subjects deemed to be protected [[Camargo, 1984](#); [Melville-Smith, 1983](#)].
- Antibodies against the hepatitis B surface antigen (anti-HBs) will be measured using ChemiLuminescence ImmunoAssay (CLIA). The cut-off of the test is set at 6.2 mIU/ml. An antibody concentration ≥ 10 mIU/ml defines seroprotection [[CDC, 1991](#)].
- Antibodies against poliovirus types 1, 2 and 3 will be determined by a virus micro-neutralisation test adapted from the World Health Organization Guidelines for WHO/EPI Collaborative Studies on Poliomyelitis [[WHO, 1993](#)]. Titres will be

expressed in terms of the reciprocal of the dilution resulting in 50% inhibition. Samples with a titre greater than or equal to 1:8 will be considered as seropositive and protective.

- Data from subjects given unconjugated Hib vaccine suggest that, in the absence of induction of immunological memory, a concentration of 0.15 µg/mL is indicative of short-term protection, with 1 µg/mL considered indicative of long-term protection [Käyhty, 1983; Anderson, 1984].
- No serological correlate of protection against pertussis has been established [Plotkin, 2010]. Antibodies against the pertussis components pertussis toxoid (PT), filamentous haemagglutinin (FHA) and pertactin (PRN) will be measured by ELISA. The seropositivity cut-off for all three pertussis antibodies in ELISA is 5 EL.U/ml. Subjects with antibody concentration below the cut-off will be considered seronegative.
- Pneumococcal serotype specific total immunoglobulin G (IgG) antibodies (antibodies to 1, 3, 4, 5, 6A, 6B, 7F, 9V, 14, 18C, 19A, 19F and 23F) will be each measured by 22F-inhibition ELISA [Concepcion, 2001] or multiplex. The antibody concentration for ELISA will be determined by logistic log comparison of the ELISA curves with a standard reference serum 89-SF available from the US Food and Drug Administration for which concentration of IgG and IgM to the serotypes are known in µg/ml [Quataert, 1995]. The cut-off for ELISA is 0.05 µg/ml. No correlate of protection is defined for the immune response to pneumococcal antigens. At the discretion of GSK Biologicals, this assay will be performed either at a GSK laboratory or at the WHO reference laboratory. The assay cut-off of the 22F-inhibition ELISA test performed at the WHO reference laboratory is 0.15 µg/ml.

The immunological assay results will be communicated to the investigator as soon as they become available.

The investigator is encouraged to share the immunological assay results for non-responders with the study subjects' parent(s)/LAR(s).

For the subjects identified as non-responders, it remains the responsibility of the investigator in charge of the subject's clinical management to determine the medical need for re-vaccination and to re-vaccinate the subjects as per local/regional practices.

## **6. STUDY VACCINES AND ADMINISTRATION**

### **6.1. Description of study vaccines**

The candidate vaccine to be used has been developed and manufactured by GSK Biologicals.

The Quality Control Standards and Requirements for the candidate vaccine are described in separate Quality Assurance documents (e.g., release protocols, certificate of analysis) and the required approvals have been obtained.

The vaccines are labelled and packed according to applicable regulatory requirements.

Commercial vaccines are assumed to comply with the specifications given in the manufacturer's Summary of Product Characteristics.

The study vaccines, formulation and presentation is detailed in [Table 9](#).

**Table 9 Study vaccines**

Treatment name	Vaccines name	Formulation	Presentation	Volume to be administered*	Number of doses
Infanrix hexa	DTPa-HBV-IPV	DT>=30IU; TT>=40IU; PT=25µg; FHA=25µg; PRN=8µg; HBsAg=10µg; Inactivated Poliovirus type 1 (Mahoney strain)=40DU; Inactivated Poliovirus type 2 (MEF-1 strain)=8DU; Inactivated Poliovirus type 3 (Saukett strain); Aluminium=700µg Al3+	The DTPa-HBV-IPV component is presented as a turbid white suspension in a pre-filled syringe.	0.5 ml *	1
	Hib	PRP=10µg; TT~=25µg Aluminium as salts = 0.12 mg	The lyophilised Hib component is presented as a white pellet in a glass vial; it must be reconstituted before use with the liquid DTPa-HBV-IPV component.		
Prevenar 13	Prevenar 13	PS1=2.2µg CRM197; PS3=2.2µg CRM197; PS4=2.2µg CRM197; PS5=2.2µg CRM197; PS6A=2.2µg CRM197; PS6B=4.4µg CRM197; PS7F=2.2µg CRM197; PS9V=2.2µg CRM197; PS14=2.2µg CRM197; PS18C=2.2µg CRM197; PS19A=2.2µg CRM197; PS19F=2.2µg CRM197; PS23F=2.2µg CRM197; AIPO 4 =125µg Al3+	Suspension for injection in a pre-filled syringe	0.5 ml	1

\*After reconstitution

## 6.2. Storage and handling of study vaccines

The study vaccines must be stored at the respective label storage temperature conditions in a safe and locked place. Access to the storage space should be limited to authorised study personnel. The storage conditions will be assessed during pre-study activities under the responsibility of the sponsor study contact. The storage temperature should be continuously monitored with calibrated (if not validated) temperature monitoring device(s) and recorded. Refer to the Module on Clinical Trial Supplies in the SPM for more details on storage of the study vaccines.

Temperature excursions must be reported in degree Celsius.

Any temperature excursion outside the range of 0.0 to +8.0°C (for +2 to +8°C/+36 to +46°F label storage condition) impacting investigational medicinal products (IMPs) must be reported in the appropriate (electronic) temperature excursion decision form ([e]TDF). The impacted IMPs must not be used and must be stored in quarantine at label temperature conditions until usage approval has been obtained from the sponsor.

In case of temperature excursion below +2.0°C down to 0.0°C impacting IMP(s) there is no need to report in (e)TDF, but adequate actions must be taken to restore the +2 to +8°C/+36 to +46°F label storage temperature conditions. The impacted IMP(s) may still be administered, but the site should avoid re-occurrence of such temperature excursion. Refer to the Module on Clinical Trial Supplies in the SPM for more details on actions to take.

Refer to the Module on Clinical Trial Supplies in the SPM for details and instructions on the temperature excursion reporting and usage decision process, packaging and accountability of the study vaccines.

## 6.3. Dosage and administration of study vaccines

The dosage and administration of study vaccines is given in [Table 10](#).

**Table 10 Dosage and administration**

(Amended 12 December 2016)

Type of contact and time point	Volume to be administered	Study group	Treatment name	Route 	Site	Side 
Visit 2 ( Day 0 )	0.5 mL	dTpa Group and Control Group	Infanrix hexa	IM	Thigh or Deltoid 	R
Visit 3 ( Day 30 )	0.5 mL	dTpa Group and Control Group	Prevenar 13	IM	Thigh or Deltoid 	L

Intramuscular (IM)

 *The vaccines should be administered in the thigh or deltoid, according to the national recommendations /local practice*

Right (R), Left (L)

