**Table 2 Study groups and treatment foreseen in the study**

(Amended 12 December 2016)

Treatment name	Vaccine name	Study Groups	
		dTpa Group	Control Group
Infanrix hexa	DTPa -HBV-IPV	x	x
	Hib	x	x
Prevenar 13	Prevenar 13	x	x

- Control: uncontrolled (*No active control or placebo. All subjects will receive the same vaccine*)
- Vaccination schedule: All subjects will receive a booster dose of *Infanrix hexa* co-administered with *Prevenar 13* between **11-18** months of age *according to the routine national/ local immunization schedule or as specified in the SPM. (Amended 12 December 2016)*
- Treatment allocation: Non-randomised. All subjects will receive a booster dose of *Infanrix hexa* co-administered with *Prevenar 13*.
- Blinding: Open-label. Note: The study personnel operating with the **GSK Biologicals' central Randomisation System on Internet (SBIR)** and the site staff will remain blinded towards the treatment allocation *of the mother in* study 116945 [DTPA (BOOSTRIX)-047]. **(Amended 12 December 2016)**

The blinding of study epoch is presented in [Table 3](#).

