##### **5.2.2.1.1. Study group and treatment number allocation**

The target will be to enrol maximum of 680 eligible subjects aged 9 months (approximately 340 subjects in each group).

After obtaining the signed and dated ICF from the subject's parent(s)/LAR(s) and having checked the eligibility of the subject, *investigator or designate will complete a standardised developmental screening tool, Ages and Stages Questionnaire-3 via a paper questionnaire (at Visit 1) with* subjects' parent(s)/LAR(s). At Visit 2, the site staff in charge of the vaccine administration will access SBIR. Upon providing the subject identification number, the randomisation system will provide the treatment number to be used for *vaccination*. **(Amended 12 December 2016)**

The number of each administered treatment must be recorded in the eCRF on the Vaccine Administration screen.

When SBIR is not available, please refer to the SBIR user guide or the Study Procedures Manual (SPM) for specific instructions.

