**Table 4 List of study procedures**

**(Amended 12 December 2016)**

Age	9 months	11-18 months	12-19 months	18 months **
Epoch	Epoch 001			
Type of contact	Visit 1	Visit 2	Visit 3	Phone contact *
Time points	Months -2 to -9	Day 0 **	Month 1 **	Day 0 to Month7 **
Sampling time points		Pre-Bst	Post-Bst	
Informed consent	●			
Check inclusion/exclusion criteria	●			
Collect demographic data		●		
Medical history, including medication/vaccine history §	●	●		
Physical examination		○		
Check contraindications and warnings and precautions		○		
Pre-vaccination body temperature		●		
Measure/record length, weight and head circumference		●		
Vaccine				
Treatment number allocation		○		
Recording of administered treatment number		●		
Vaccine administration		●		
Laboratory assays				
Blood sampling for antibody determination (approx 5 mL)		●	●	
Safety assessments				
Record any concomitant medication/vaccination		●	●	
Record any intercurrent medical conditions			●	
Distribution of diary cards		●		
Recording of solicited adverse events (Day 0-Day 3) post-vaccination by subjects' parent(s)/LAR(s) in the diary card		●		
Recording of non-serious adverse events within 31 days (Day 0-Day 30) post-vaccination, by subjects' parent(s)/LAR(s) in the diary card		●	●	
Recording of large injection-site reactions		●		
Return of diary cards			○	
Diary card transcription by investigator or site staff			●	
Recording of neurodevelopmental status by the subjects' parent(s)/LAR(s) in the ASQ-3 paper questionnaire	●	● **	● **	● **
Transcribe the information in ASQ-3 paper questionnaire, by the investigator	●	● **	● **	● **
Recording of SAEs and AEs/SAEs leading to withdrawal	●	●	●	● **
Recording of SAEs related to study participation or to a concurrent GSK medication/vaccine	●	●	●	●
Study Conclusion †				●

● is used to indicate a study procedure that requires documentation in the individual eCRF.

○ is used to indicate a study procedure that does not require documentation in the individual eCRF.

\* **For Czech Republic, the phone call at 18 months may be replaced by a clinic visit if deemed preferable by the study team.**

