### **6.7.1. Recording of concomitant medications/products and concomitant vaccinations**

The following concomitant medication(s)/product(s)/vaccine(s) must be recorded in the eCRF.

- All concomitant medications/products, except vitamins and dietary supplements, administered during the period starting from the administration of the dose of study vaccines (Visit 2) and ending at Visit 3 (**Day 0 to Day 30**)
- Any concomitant vaccination administered in the period starting from the administration of the dose of study vaccines (Visit 2) and ending at the study visit 3 (**Day 0 to Day 30**).

Note: Medications/vaccinations listed prior to the dose of study vaccine are to be recorded as medical/vaccination history.

- Prophylactic medication (i.e., medication administered in the absence of ANY symptom and in anticipation of a reaction to the vaccination).

E.g., an anti-pyretic is considered to be prophylactic when it is given in the absence of fever and any other symptom, to prevent fever from occurring [fever is defined as temperature  $\geq 37.5^{\circ}\text{C}/99.5^{\circ}\text{F}$  for oral, axillary or tympanic route, or  $\geq 38.0^{\circ}\text{C}/100.4^{\circ}\text{F}$  for rectal route].

- Any concomitant medications/products/vaccines listed in Section 6.7.2.
- Any concomitant medications/products/vaccines relevant to a SAE to be reported as per protocol or administered at any time during the study period for the treatment of a SAE. In addition, concomitant medications relevant to SAEs need to be recorded on the expedited Adverse Event report.

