 - dTpa Group: This group will consist of infants born to mothers belonging to the dTpa Group in study 116945 [DTPA (BOOSTRIX)-047] i.e., mothers who received a single dose of *Boostrix* during pregnancy and a dose of placebo immediately post-delivery and infants who received full primary vaccination course as per protocol requirement in the study 201330 [DTPA (BOOSTRIX)-048 PRI]. All subjects in this group will receive a booster dose of *Infanrix hexa* co-administered with Prevenar 13 according to the routine national/ local immunization schedule or as specified in the SPM.
 - Control Group: This group will consist of infants born to mothers belonging to the Control group in study 116945 [DTPA (BOOSTRIX)-047] i.e., mothers who received a single dose of placebo during pregnancy and a dose of *Boostrix* immediately post-delivery and infants who received full primary vaccination course as per protocol requirement in the study 201330 [DTPA (BOOSTRIX)-048 PRI]. All subjects in this group will receive a booster dose of *Infanrix hexa* co-administered with Prevenar 13 according to the routine national/ local immunization schedule or as specified in the SPM.

Table 1 Study groups and epoch foreseen in the study

Study groups	Number of subjects*	Age (Min/Max)**	Epoch
			Epoch 001
dTpa Group	340	11 months-19 months	x
Control Group	340	11 months-19 months	x

*Maximum number of subjects

**Age at the time of vaccination depending on routine national/ local immunization schedule or as specified in the SPM

The study groups and treatment foreseen in the study is presented in [Table 2](#).

Table 2 Study groups and treatment foreseen in the study

Treatment name	Vaccine name	Study Groups	
		dTpa Group	Control Group
Infanrix hexa	DTPa-HBV-IPV	x	x
	Hib	x	x
Prevenar 13	Prevenar 13	x	x

- Control: uncontrolled (No active control or placebo. All subjects will receive the same vaccine)
- Vaccination schedule: All subjects will receive a booster dose of *Infanrix hexa* co-administered with *Prevenar 13* between 11-18 months of age according to the routine national/ local immunization schedule or as specified in the SPM.
- Treatment allocation: Non-randomised. All subjects will receive a booster dose of *Infanrix hexa* co-administered with *Prevenar 13*.

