4.1.4. According-to-protocol cohort for analysis of immunogenicity

The ATP cohort for analysis of immunogenicity will include all evaluable subjects from the ATP cohort for analysis of safety:

- Who meet all eligibility criteria.
- Who received all doses of vaccine in the primary study 201330 [DTPA (BOOSTRIX)-048 PRI].
- Who comply with the procedures and intervals defined in the protocol (refer to Table 5 of the protocol).
- Who do not meet any of the criteria for elimination from an ATP analysis (refer to Section 6.7.2 of the protocol).
- Who did not receive a product leading to elimination from an ATP analysis as listed in Section 6.7.2 of the protocol,
- Who did not present with a medical condition leading to elimination from an ATP analysis as listed in Section 6.8 of the protocol,
- For whom data concerning immunogenicity endpoint measures are available. This will include subjects for whom assay results are available for antibodies against at least one study vaccine antigen component after vaccination.
- The interval between the vaccination visit and post-booster blood sampling, considered for inclusion of a subject will be 21–48 days.

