1070	Vaccination not according to protocol Site or route of study vaccine administration wrong or unknown. Also inherited from the 048 study.	Visit 2	Safety, immunology
1080	Vaccine temperature deviation (vaccine administration not as per protocol) => Infanrix hexa vaccine administered despite a Good Manufacturing Practices (GMP) no-go temperature deviation. Also inherited from the 048 study.	Visit 2	Safety, immunology
1090	Expired vaccine administered (vaccine administration not as per protocol)=> Subjects who received an expired Infanrix hexa . Also inherited from the 048 study.	Visit 2	Safety, immunology

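### Protocol Table 10 places Prevenar 13 at Visit 3 (Day 30), whereas the rest of the plan has it given together with Infanrix hexa at Visit 2 (Day 0)

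*Protocol*

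**What the plan says.** Table 10 is the dosing table. Protocol Section 5.6.2.11 sends sites to Section 6.3 for administration details, and Section 6.3 consists of that table. Its first row gives Infanrix hexa at Visit 2 (Day 0). Its second row reads "Visit 3 ( Day 30 ) 0.5 mL dTpa Group and Control Group Prevenar 13". Both rows apply to both groups.

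Elsewhere the plan describes one vaccination occasion:

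- Protocol Section 3, on vaccination schedule and treatment allocation: "All subjects will receive a booster dose of *Infanrix hexa* co-administered with *Prevenar 13". Section 1.2.2 also calls Prevenar 13 a co-administered vaccine.
- SAP Section 2, for each group: "co-administered with Prevenar 13 according to the routine national/ local immunization schedule or as specified in the SPM".
- Protocol Table 4 marks treatment number allocation, the row "Recording of administered treatment number" and vaccine administration in the Visit 2 column only.
- Protocol Section 5.2.2.1.1: "At Visit 2, the site staff in charge of the vaccine administration will access SBIR". Section 5.6.2.9 likewise allocates treatment numbers at Visit 2.
- Protocol Section 6.7.1 sets the concomitant-medication period as "starting from the administration of the dose of study vaccines (Visit 2) and ending at" Visit 3, so Visit 3 closes the period and is not a dosing visit.

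**The concern.** A site cannot follow both Table 10 and Table 4 for Prevenar 13. The error sits in an operative instruction, in the table a site would open to see what to inject and when.

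Visit 3 is also the visit at which the post-booster sample is drawn, and its read-outs include all 13 pneumococcal serotypes (Table 8). If Prevenar 13 were given then, the secondary endpoints defined one month after the booster would have no booster behind them for those serotypes. Reactogenicity of Prevenar 13 is part of a secondary objective too, yet diary cards are handed out only at Visit 2 (Table 4, Section 5.6.2.14).

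**Working it through.** No power, alpha or precision figure depends on this cell, so the check compares texts and adds one interval calculation.

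**Timing of Prevenar 13 by source**

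| Source | Timing |
|---|---|
| Protocol Table 10 | Visit 3, Day 30 |
| Protocol Sections 1.2.2 and 3 | With Infanrix hexa |
| Protocol Table 4 | All vaccination steps at Visit 2; none at Visit 3 |
| Protocol Sections 5.2.2.1.1 and 5.6.2.9 | Treatment number obtained at Visit 2 |
| Protocol Sections 5.6.2.6 and 5.6.2.14 | Visit 2 named as the vaccination visit |
| Protocol Section 6.7.1 | Study vaccines, plural, at Visit 2 |
| SAP Section 2 | With Infanrix hexa |
| SAP Section 4.2.3.1, code 2090 | Sampling interval counted from vaccination at Visit 2 |

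The Table 10 cell stands alone. The references to the national schedule or the SPM do not reconcile it, because those sentences still describe co-administration and Table 10 fixes Visit 3 for every infant in every country.

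**Interval to the post-booster bleed.** Inputs: the bleed is at Visit 3, and Table 5 allows 21 to 48 days from Visit 2 to Visit 3 (optimum 30).

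- Prevenar 13 at Visit 2: Visit 3 − Visit 2 = 21 to 48 days, as the endpoints intend.
- Prevenar 13 at Visit 3: Visit 3 − Visit 3 = 0 days.
- Infanrix hexa at Visit 2 in both cases: 21 to 48 days, unchanged.

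**Endpoints touched under literal use**

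- Post-booster pneumococcal read-outs, all secondary: 13 of 13 lose their meaning as a booster response.
- Pre-booster pneumococcal read-outs: 0 of 13, because that sample precedes both vaccines.
- Primary antigens: 7 seroprotection (diphtheria, tetanus, HBs, polio 1, 2 and 3, PRP) + 3 booster response (PT, FHA, PRN) = 10. The sampling interval changes for none of them.

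An unchanged interval does not show that those ten are unaffected. Prevenar 13 is conjugated to CRM197, a diphtheria protein (Trademarks, Table 9), and anti-diphtheria seroprotection is a primary endpoint. An infant given Prevenar 13 a month late has a diphtheria response measured without that co-administered carrier.

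**The case against.** The strongest reply is that this is a typing slip with no real ambiguity. The protocol is a single-dose booster study (Section 6.5), and a site attempting Visit 3 dosing would find no treatment-number step and no diary card planned for that visit. All analyses are descriptive, and only secondary pneumococcal read-outs would clearly lose meaning. This largely stands: the intended visit is clear and the practical effect is probably nil. It does not make the dosing table correct.

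Three stronger readings are tempting, and the documents do not support them.

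- *The SAP would let such an infant through.* Code 2090 counts from Visit 2, code 2080 is only carried forward from study 048, and the stated condition of code 1070 is "Site or route of study vaccine administration wrong or unknown". However, code 1070 has a broader heading about vaccination departing from the protocol. The ATP safety cohort (protocol 10.4.3, SAP 4.1.3) requires compliance with vaccine administration and receipt of the booster of the study vaccines. The ATP immunogenicity cohort is a subset of it and adds "Who comply with the procedures and intervals defined in the protocol (refer to Table 5 of the protocol"). Table 5 names no vaccine, but the safety-cohort condition does not depend on Table 5.
- *A definite number of follow-up days would be lost.* With windows fixed at Visit 2, the solicited period (Days 0 to 3) would be over before the earliest Visit 3 on Day 21, and at most 30 − 21 + 1 = 10 of the 31 unsolicited days would remain. But Section 8.2.1 ties AE recording to administration of the study vaccines, and SAEs are collected until discharge. The supportable statement is narrower: no diary card is issued at Visit 3.
- *Only the pneumococcal results of such an infant need be dropped.* That conflicts with the administration-compliance condition and, given the CRM197 carrier, has no stated basis for the primary antigens.

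**Conclusion.** The Prevenar 13 cell of Table 10 is wrong as written and should read Visit 2 (Day 0). If it were followed literally, the interval from Prevenar 13 to the bleed would be 0 days instead of 21 to 48, and all 13 secondary post-booster pneumococcal read-outs for that infant would fail to measure a booster response.

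The realised effect is probably nil. The documents give no count of infants dosed at Visit 3, and the Visit 2 treatment-number step and the co-administration text make it unlikely that there are any. Sample size, the precision in Table 16 and the primary endpoint definitions are unchanged. A reader should not infer that the pneumococcal results are compromised. What remains open is whether any site acted on the cell. The SPM might have settled this for sites, but it is not among the documents.

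**What to change.** - Change the Prevenar 13 cell of Table 10 to Visit 2 (Day 0). If vaccination is still under way, send sites a short clarification.
- The SAP of March 2019 already refers to enrolment by country (Section 5.3.2), so vaccination may be complete. In that case, confirm from the existing vaccine administration records the visit at which Prevenar 13 was given, for example by adding visit to the dose summary by vaccine in SAP Section 5.2.2.
- List any infant given Prevenar 13 at Visit 3 and treat that infant as not compliant with vaccine administration under the existing ATP rules (protocol 10.4.3 and 10.4.4, SAP 4.1.3 and 4.1.4). Do not remove the pneumococcal results alone. Correcting the cell matters here because, as printed, Table 10 could be cited to call such an infant compliant.

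The cost is one table cell, one site clarification if still needed, one check of data already collected, and one line in the study report.
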